4.2 INCLUSION CRITERIA

Adults (patients aged above 18) undergoing cross sectional imaging that includes their abdomen.

Mobile patients, able to consent and volunteer their participation in the study.

4.3 EXCLUSION CRITERIA

Patients with uncorrected abdominal wall hernias or abdominal wall defects excluded as anatomical deviations from the norm can result in incorrect estimates of abdominal wall depth.

4.4 WITHDRAWAL CRITERIA

Free to withdraw at any time, without giving a reason at the point of measuring the physical body measurements.

5. ADVERSE EVENTS

5.1 DEFINITIONS

There are no adverse events anticipated form the taking of physical body measurements.

5.2 REPORTING PROCEDURES

All adverse events, if ever they should arise, although non anticipated, will be reported.

5.2.1 Non serious AEs

These will be recorded.

5.2.2 Serious AEs

An SAE form should be completed and faxed to the Chief Investigator within 24 hours. However, relapse and death due to <condition>, and hospitalisations for elective treatment of a pre-existing condition do not need reporting as SAEs.

All SAEs should be reported to the <name of REC> where in the opinion of the Chief Investigator, the event was:

- 'related', i.e. resulted from the administration of any of the research procedures; and
- •'unexpected', i.e. an event that is not listed in the protocol as an expected occurrence

Reports of related and unexpected SAEs should be submitted within 15 days of the Chief Investigator becoming aware of the event, using the NRES SAE form for non-IMP studies. The Chief Investigator must also notify the Sponsor of all SAEs.

Local investigators should report any SAEs as required by their Local Research Ethics Committee, Sponsor and/or Research & Development Office.

Contact details for reporting SAEs

Email: [contact] attention [name]

Please send SAE forms to: [contact]

[contact] (Mon to Fri 09.00 – 17.00)

6. ASSESSMENT AND FOLLOW-UP

No follow up will be made

7. STATISTICS AND DATA ANALYSIS

Sample size calculation has proceeded using an online calculator (2). With a confidence interval of 95%, population size of 56 million(England, 2018), standard deviation of 5%. This gives an ideal sample size of 385.

Data collected will be subjected to correlational mathematic analyses using 'R' software package for statistical analysis.

No formal statistician input is required for this which is within the academic expertise of the PhD student applicant.

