2. STUDY OBJECTIVES

2.1 Primary Objectives

- 2.11. Investigate the correlation between waist circumference and abdominal wall depth through physical data collection. Waist circumferences will be obtained from patients as actual physical measurements and not estimated while the abdominal wall depth will be ascertained from each patient's corresponding cross sectional image.
- 2.12 Measure the abdominal wall depth of each participant from their cross sectional image. During laparoscopy, patients are in the same supine position and with patients required to be still during their scan, a reliable depth measurement can be taken as a proxy for their actual abdominal wall depth.

Produce descriptive statistics of the depths in the cohort of patients. Group each 1cm of abdominal wall depths by categories of waist circumference

2.13. Produce a nomogram for use as a predictor of abdominal wall depth.

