3. STUDY DESIGN

Quantitative Observational Study (Cross Sectional Study)

Participant physical measurements (waist circumference (cm), height(cm), weight(kg)) and the depth in centimetres of the associated abdominal wall depth taken from the corresponding radiological image.

These variables will be subjected to mathematical analysis in establishing correlations and building a nomogram.

A minimum of 385 participants and associated radiological scans of various weights(kg) will be recruited on a rolling basis. Recruitment will be at the time of patient presentation for their scan in the radiology department.

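### The calculation in section 7 matches a survey formula for one proportion, with its 5% margin called a standard deviation, so it does not justify 385 for a correlation, equation and nomogram

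*Protocol*

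**What the plan says.** Section 7 takes the number from a general online sample-size calculator (reference 2) and reports three inputs and the result: "With a confidence interval of 95%, population size of 56 million(England, 2018), standard deviation of 5%. This gives an ideal sample size of 385". It names no expected proportion, margin of error, power, expected correlation, SD of depth or tolerable prediction error.

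The number is used elsewhere. The trial summary repeats it, section 3 makes it a floor ("A minimum of 385 participants and associated radiological scans"), and the schedule of events in section 14.4 ends the study once the sample size is reached.

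The aims are of a different kind. The first primary objective in section 2.1 is to "Investigate the correlation between waist circumference and abdominal wall depth through physical data collection", two continuous measurements in cm. Sections 2.1 and 3.1 add an equation linking the two and a nomogram by waist category. Section 2.2 adds a comparison with BMI.

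**The concern.** The figure is the familiar answer to a survey question about a percentage, and no objective asks such a question. One input carries the wrong name: a standard deviation describes the spread of a measurement, whereas the 5% appears to be the tolerated error in a percentage. The 95% is a confidence level, not an interval.

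This is the only planning calculation in the protocol, and its result is called ideal. A reader could take that to mean that someone had considered how precisely 385 people locate the correlation or the nomogram's limits. Nothing in the calculation addresses either. The nomogram is meant to inform needle insertion, so the precision of its limits, especially at small and large waists, is what its users would need to know.

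**Working it through.** **1. Reproducing the protocol's figure.** Inputs from section 7: 95% confidence (z = 1.96), N = 56,000,000 and 5%. Assumed: p = 0.5, with the 5% taken as the margin e.

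- n₀ = z² p(1 − p) / e² = 1.96² × 0.25 / 0.0025 = 384.16 (384.146 with unrounded z).
- Finite-population correction: n = n₀ / (1 + (n₀ − 1)/N) = 384.143, rounded up to 385.

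The match is exact. The 56 million moves n by 384.146 − 384.143 ≈ 0.003. It is also the population of England, whereas the study samples mobile, consenting adults having abdominal imaging.

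**2. The inputs as literally worded.** For a mean, n = (z × SD / half-width)². Section 7 gives an SD of 5% and no half-width, so no n follows. A half-width of 0.5 points would return (1.96 × 5 / 0.5)² = 384.16, but the protocol states no such half-width.

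**3. What 385 gives for the correlation.** Assumptions: complete waist–depth pairs, illustrative r, and Fisher's z with SE = 1/√(385 − 3) = 1/√382.

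| r | 95% CI | half-width |
|---|---|---|
| 0.3 | 0.21 to 0.39 | 0.091 |
| 0.5 | 0.42 to 0.57 | 0.075 |
| 0.7 | 0.65 to 0.75 | 0.051 |
| 0.8 | 0.76 to 0.83 | 0.036 |

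Smallest r detectable with 90% power, two-sided 5%: tanh((1.96 + 1.2816)/√382) = 0.164.

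**4. What 385 gives for prediction limits from a linear regression.** Assumptions: a straight line, with normal residuals of constant SD. At a waist k SDs from the mean, the 95% half-width for the position of a 95% prediction limit, in residual SDs, is about 1.96 × √((1 + k²)/n + 1.96²/(2(n − 1))).

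- Mean waist (k = 0): 1.96 × √(0.00260 + 0.00500) = 0.17.
- 2 SD from the mean (k = 2): 1.96 × √(0.01299 + 0.00500) = 0.26.

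**5. Limits set separately in each waist category.** The protocol gives no number of categories, so 5 or 10 equal ones are assumed (385/5 = 77; 385/10 ≈ 38). The formula with k = 0, in within-category SDs, gives:

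- n = 77: 1.96 × √(0.01299 + 0.02527) = 0.38.
- n = 38: 1.96 × √(0.02632 + 0.05191) = 0.55.

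**The case against.** **385 may be perfectly adequate.** A reader might infer from a wrong justification that the study is too small. The documents do not support that. For detecting a correlation 385 is ample, and at r = 0.7 it gives a half-width of about 0.05. For the nomogram, the protocol gives no SD of depth, tolerable error in cm or number of categories, so adequacy can be neither shown nor denied. This objection stands, and the point is confined to the justification.

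**The source formula is inferred.** Section 7 does not state p = 0.5, and step 2 shows another combination that returns 385. That is fair. The survey formula is much the likelier source, because it uses the 5% directly, has a place for the population size and fits a general calculator. Either way an essential input is missing from the text.

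**The stated inputs might be said to give some other number.** A reader could derive 73 from a 5% proportion with a ±5-point margin, or 4 from an SD of 5% with a 5-point margin. Neither reading is in the protocol, which states no proportion and no margin. As worded, the inputs give no number at all.

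**Restating precision at a fixed n is justification after the fact.** This is partly true. It sets no target and gives no figure for the waist-versus-BMI comparison, which depends on a waist–BMI correlation that the protocol does not supply. It does replace an irrelevant basis with a true statement of what the planned number delivers.

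**A statistical analysis plan may exist.** It would not settle the matter, because the protocol itself states the calculation and its inputs.

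**Conclusion.** The concern holds as a fault in the justification. The stated calculation matches the size for one proportion within ±5 points, labels a margin of error as a standard deviation, and uses a population that is neither the one sampled nor of any numerical consequence. It contains nothing about the correlation, the equation or the nomogram.

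It does not follow that the number recruited is wrong. What is lost is an accurate account of precision, and that account is uneven: good for r, less favourable for prediction limits away from the mean waist (±0.26 against ±0.17 residual SD), and weaker again if limits are set by category. These sizes rest on p = 0.5 as the inferred input, complete pairs, illustrative values of r, a linear model with constant normal residuals, and assumed equal categories.

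**What to change.** Keep the planned 385 and replace the sample-size paragraph in section 7 with wording along these lines:

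> The study will recruit at least 385 participants. If all contribute both a waist and a depth measurement, then at a 95% confidence level the half-width of the interval for r is about 0.09, 0.075, 0.05 and 0.036 for illustrative r of 0.3, 0.5, 0.7 and 0.8. The 95% prediction limits from a linear regression of depth on waist are located to about ±0.17 residual SD at the mean waist and ±0.26 at 2 SD from it. If limits are instead set separately by waist category, precision is lower: about ±0.38 SD with 77 per category and ±0.55 SD with 38, assuming 5 or 10 equal categories.

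Delete the population size, the 5% standard deviation and the word *ideal*, and write *confidence level* for *confidence interval*.

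The cost is protocol wording only, with no change in recruitment. The sponsor would be accepting a stated basis that is openly less favourable at the extreme waists.

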13. REFERENCES

14. APPENDICES

GLOSSARY OF ABBREVIATIONS

WC weight circumference

AWD abdominal wall depth

TRIAL SUMMARY

TRIAL TITLE

Investigating whether the abdominal waist circumference or abdominal girth can be employed as an accurate estimate of abdominal wall depth.

SHORT TITLE

Investigating whether the waist circumference can be used as an estimator of the depth of the abdomen as measured from the belly button.

DESIGN

Observational Study (Correlational Research)

AIMS

To assess the correlation between abdominal wall depth and waist circumference

To use this information in establishing a nomogram according to weight circumference for recommended Veres needle entry depth.

OUTCOME MEASURES

At the end of the study, it will be expected that the following will have been achieved

- 1. Production of correlation equation connecting waist circumference and abdominal wall depth
- 2. Description of weight relationship to abdominal adiposity.
- 3. Establishment of a safety nomogram guiding Veres needle insertion according to category of body waist circumference.

POPULATION ELIGIBILITY

Any mobile adult patient undergoing elective abdominal Computed Tomography Imaging (CT) or Magnetic Resonance Imaging (MRI) scans.

SAMPLE SIZE

385

[figure not shown]
DURATION

1 month

FUNDING AND SUPPORT IN KIND

(Names and contact details of ALL organisations providing funding and/or support in kind for this trial)	FINANCIAL AND NON FINANCIALSUPPORT GIVEN
EPSRC Digital Health and Care Centre for Doctoral Training (UKRI funded CDT)	PhD Studentship at the University of Bristol

TRIAL FLOW CHART

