1.2 RATIONALE FOR CURRENT STUDY

This study seeks to assess whether the waist circumference can estimate the abdominal wall depth to a reliable degree of accuracy so as to be incorporated in a nomogram that would categorise suggested Veres needle abdominal insertion depth according to waist circumference range.

The research question is therefore 'Can the waist circumference be employed as an estimate of the abdominal wall depth?'

This would be helpful in guiding initial Veres entry into the abdominal cavity during laparoscopic (key-hole) or robotic surgery where entry is achieved blind without standardised depth advice. The traditional Body Mass Index (BMI) will also be taken to see if it makes a better correlation than abdominal girth. A study has previously been carried out analysing the relationship between BMI and vertical distance between umbilicus and retroperitoneal vessels (1) but we hypothesise waist circumference may be a better measure. The abdominal wall depth will be measured directly from abdominal Computed Tomography (CT) or Magnetic Resonance Imaging (MRI) scans with the waist, weight and height measurements to be physically taken from eligible consenting participants. The existence of a relationship that can be reliable in guiding needle depth investigation is hypothesised and requires further investigation.

Due to urgent need for safety mechanisms to be incorporated in the conduct of laparoscopic abdominal wall injury, this study attempts to provide some guidance into how deep the Veres needle should be inserted when a Veres needle is being used as the first entry abdominal device and insufflator. The study is aiming to improve safety in laparoscopic entry where a Veres needle is used by providing insertion depth guidance. It is aimed to reduce the number of failed entries or complicated entries.

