3.1 STUDY OUTCOME MEASURES

- 3.12 Production of correlation equation connecting waist circumference and abdominal wall depth
- 3.13 Description of weight relationship to abdominal adiposity.
- 3.14 Establishment of a safety nomogram guiding Veres needle insertion according to category of body waist circumference.

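### The aim is accurate estimation of an individual's abdominal wall depth, but the named analysis is correlation and no prediction error in centimetres is specified

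*Protocol*

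**What the plan says.** **The aim is accuracy.** The trial title asks whether waist circumference "can be employed as an accurate estimate of abdominal wall depth". Section 1.2 asks whether "waist circumference can estimate the abdominal wall depth to a reliable degree of accuracy so as to be incorporated in a nomogram". Objective 2.13 is a nomogram meant to predict depth, and outcome 3.14 is a safety nomogram for needle insertion by waist category.

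**The analysis is correlation.** Objective 2.11 is to "Investigate the correlation between waist circumference and abdominal wall depth through physical data collection". Outcome 3.12 is "Production of correlation equation connecting waist circumference and abdominal wall depth". The whole account of the analysis in section 7, apart from naming R as the software, is: "Data collected will be subjected to correlational mathematic analyses".

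**Outputs in centimetres.** Objective 2.12 plans descriptive statistics of depth, with 1 cm depth groups set against waist categories.

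**BMI.** Section 1.2 says: "The traditional Body Mass Index (BMI) will also be taken to see if it makes a better correlation than abdominal girth". Objective 2.21 asks whether BMI is the inferior proxy. Neither place says how uncertainty in the comparison will be handled.

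The protocol gives no SD of wall depth, expected correlation, residual error, prediction limits or acceptable error.

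**The concern.** Whether waist circumference is accurate enough to guide a needle depends on how far one patient's true depth may lie from the depth read off the nomogram, in centimetres. A correlation coefficient does not say that. It is a unitless ratio of explained to total spread, so recruiting a wider range of waists raises it without making any single prediction better.

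A fitted line by itself does not close the gap. It gives the mean depth at a given waist, so with roughly symmetric scatter about half of patients are deeper than the value shown.

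The study could therefore follow the protocol to the letter, report a strong and precisely estimated correlation, and issue a nomogram of mean depths with the accuracy question untested. The nomogram is intended for an entry that the protocol itself describes as blind, so the size of the individual error is the result that its users would need most.

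**Working it through.** **1. The plan's own figure.** Section 7 gives n = 385. The usual formula for estimating a proportion, with p = 0.5 (assumed) and the stated 5% read as a margin of error, gives 1.96² × 0.25 / 0.05² = 384.16, rounded up to 385. The figure reproduces, but it carries no information about prediction error. It is used below only as the sample size.

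**2. How convincing a correlation would look at n = 385.** On Fisher's z scale the standard error is 1/√382.
- Smallest r significant at the two-sided 5% level: tanh(1.96/√382) = 0.10.
- 95% confidence interval for an observed r of 0.8: about 0.76 to 0.83.

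**3. What r implies for one patient.** Residual SD = SD × √(1 − r²). The 95% prediction half-width is about 1.96 times that; at n = 385 the exact factor, 1.966 × √(1 + 1/385), changes little. At r = 0.8, √(1 − 0.64) = 0.60 and the half-width is 1.96 × 0.60 = 1.18 SD, against 1.96 SD with no predictor.

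The SD and r below are assumptions, because the protocol gives neither. Half-widths are in cm:

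| SD of depth | r = 0.5 | r = 0.7 | r = 0.8 | r = 0.9 |
|---|---|---|---|---|
| 0.5 cm | 0.85 | 0.70 | 0.59 | 0.43 |
| 1.0 cm | 1.70 | 1.41 | 1.18 | 0.86 |
| 1.5 cm | 2.56 | 2.11 | 1.77 | 1.29 |

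The half-width passes 1 cm when SD > 1/(1.96 × √(1 − r²)), which is about 0.71 cm at r = 0.7, 0.85 cm at r = 0.8 and 1.17 cm at r = 0.9. At an SD of 0.5 cm it never does: even with r = 0 it is 1.96 × 0.5 = 0.98 cm.

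**4. r depends on who is recruited.** Take one fixed line with slope 0.05 cm of depth per cm of waist and residual SD 0.6 cm (both assumed). Then r = 0.05s/√((0.05s)² + 0.6²), where s is the SD of waist.
- s = 8 cm: 0.40/√(0.16 + 0.36) = 0.55.
- s = 20 cm: 1.00/√(1.00 + 0.36) = 0.86.

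The error in centimetres is the same in both.

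**5. If spread grows with depth.** Simulation with assumed inputs: waist normal with mean 95 and SD 15 cm, mean depth 2.5 + 0.05 × (waist − 95) cm, coefficient of variation 25%. Limits of constant width, ±1.96 residual SD, cover about 94 to 95% of all patients. For waists above 110 cm they cover about 84% with normal errors and 86% with lognormal errors.

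**6. BMI comparison.** Both correlations come from the same patients, so the variance of their difference needs the covariance. Assume r₁ = 0.60 for waist, r₂ = 0.55 for BMI and r₁₂ = 0.85 between the two.
- (1 − r₁²)² + (1 − r₂²)² = 0.4096 + 0.4865 = 0.8961.
- c = r₁₂(1 − r₁² − r₂²) − ½r₁r₂(1 − r₁² − r₂² − r₁₂²) = 0.85 × 0.3375 + 0.165 × 0.385 = 0.3504.
- Paired SE = √((0.8961 − 2 × 0.3504)/385) = 0.0225.
- SE if wrongly treated as independent = √(0.8961/385) = 0.048.
- Power for the difference of 0.05 at the two-sided 5% level: about 60% paired, 18% as independent.

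**The case against.** **Detail of this kind may sit in an analysis plan that is not shown.** Residual SD, the choice of regression model and the test for two correlations are often left there, and section 7 does not exclude regression. This stands as far as technical detail goes. It does not remove the mismatch, because the protocol itself words an objective, an outcome and its statistics section as correlation while its title and rationale ask about accuracy. An analysis plan faithful to that wording would inherit the problem.

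**The protocol goes beyond a coefficient.** It plans an equation, 1 cm depth groups by waist category and a predictive nomogram. These imply a fitted line and output in centimetres, from which residual error could be derived. This also stands. It would be wrong to say that the study will produce nothing in centimetres, or that r is its declared test of success; no such criterion is written. What remains is that nothing requires the individual error to be estimated or reported.

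**Stronger readings that the text does not support.** A reader might infer three things.
- *That correlation cannot show whether BMI is the weaker proxy.* It can. With the same patients and outcome, the larger r from a linear predictor is the smaller residual SD.
- *That the protocol picks whichever r is larger.* It states no such rule and does not rule out an interval or a test.
- *That prediction error will exceed a centimetre.* That depends on an SD that the protocol does not give.

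**Conclusion.** The point holds in this form: the protocol asks whether waist circumference estimates an individual's depth accurately enough for a needle-depth nomogram, names correlation as the analysis, and specifies no prediction error in centimetres.

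One result needs no assumption about the SD. Under a linear model with constant normal scatter, r = 0.8 leaves a 95% prediction range 60% as wide as with no predictor at all. In centimetres the size is conditional: ±0.6 to ±1.8 cm for an assumed SD of 0.5 to 1.5 cm. The coverage of about 84 to 86% above 110 cm rests on the assumed waist distribution, slope and 25% coefficient of variation. It shows why constant-width limits should not be taken for granted, and is not a forecast for this study.

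On BMI, the gap is narrower: comparing correlations is a legitimate method, but nothing ties the conclusion to a paired measure of uncertainty. The 60% and 18% power figures depend on the three assumed correlations.

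**What to change.** - **Section 7:** make the primary analysis a regression of depth on continuous waist circumference. Allow spread to vary with waist, by modelling log depth or by quantile regression. Report the residual SD and 95% prediction limits in cm. Keep r as a descriptive figure.
- **Outcome 3.12:** reword it as a prediction equation with 95% prediction limits.
- **Objective 2.21:** base the conclusion on a paired, same-patient 95% confidence interval for the waist-minus-BMI difference in residual SD or in r, for example by bootstrapping patients. Call BMI inferior only if that interval excludes zero in waist's favour.

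**Cost:** wording changes and slightly more analysis in R, with no extra participants or measurements. The reported accuracy will look less favourable than r alone. The changes should be made before the data are analysed, so that the measure of accuracy is not chosen after the correlation is known.
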